This study will be a single-center study of healthy volunteers conducted at Houston Methodist Hospital. We will enroll 15 participants who are >18 and <35 years of age and 15 participants who are ≥60 years of age. The rationale for the age distribution is to obtain information from people who are considered healthy by ASA criteria 1 and people who meet ASA criteria 2. Participants who are >18 to 35 years of age are a) more likely to have experienced VR software previously and b) more likely to meet ASA criteria 1. Participants who are >60 years of age are a) less likely to have experienced VR software previously and b) more likely to meet ASA criteria 2. These older participants are considered similar to the target population of a proposed subsequent conventional clinical trial; however, it is possible that participants in the younger age group (>18 to 35 years of age) may meet ASA criteria 2.

A total of 30 participants will be prospectively enrolled. All participants will be given post-use surveys to assess usability and efficacy outcomes.

Inclusion Criteria:

1. Healthy volunteers >18 years of age who meet one of the following criteria:
 - a. **ASA 1:** A normal healthy patient. Example: Fit, nonobese (BMI under 30), a nonsmoking patient with good exercise tolerance.
 - b. **ASA 2:** A patient with mild systemic disease. Example: Patient with no functional limitations and a well-controlled disease (eg, treated hypertension, obesity with BMI under 35, frequent social drinker, but is nonsmoking).
2. Person without underlying cognitive disorder or associated phobias (eg. claustrophobia).

Exclusion Criteria:

1. Person with active psychiatry disorders, especially schizophrenia
2. Person who is deaf or blind.

11. Screening and Recruitment

All participants will be screened by the principal investigator and clinical research staff, who have been trained in the clinical investigational plan, to determine if the potential participant is eligible for enrollment. Potential participants will be assigned a screening number which will be recorded in an excel sheet; all participants who receive the study intervention during the study will be noted. All participants must meet eligibility criteria (and if not, which eligibility criteria were not met will be recorded); reasons for not meeting enrollment criteria or receiving study intervention will be recorded. No participants belonging to a vulnerable population will be enrolled.

During the informed consent process, the investigator or designee, who has been trained on the protocol, will explain the nature and scope of the intervention, potential risks, and benefits of

participation and answer questions from the potential participants. All participants will sign and date the Institutional Review Board (IRB)/Ethics Committee (EC) approved informed consent form before any study-specific procedures are performed. In addition, the signed informed consent will be retained with the research records, and a copy will be given to the participant.

Healthy Participants will be identified:

1. Through public advertisement sent via flyers posted around Texas Medical Center and mass emails to public domain emailing lists for example, University of Houston and Rice University, available to the local Houston population.

No medical records will be reviewed for this healthy volunteer study. Medical history obtained will be from participant self-report.

12. Withdrawal of Subjects

Participants will be withdrawn from the study if they do not receive any study interventions. At the moment of withdrawal, all data related to participant will be removed from the corresponding excel documents and waivers will be shredded.

A participant may discontinue his or her participation without giving a reason at any time during the study. For example, the Principal Investigator may withdraw a participant due to failure to comply with pilot study intervention requirements, or the participant is uncooperative or refuses to continue in the study intervention.

13. Provisions to Protect the Privacy Interests of Subjects

Only the minimum amount of personal information needed to conduct this study will be collected regarding participants' privacy interests. Study participants will be informed that the only individuals who can see un-coded personal health information include the following: the Study Doctor, other employees who work on this study (including the Institutional Review Board) at the hospital, employees of the sponsor who check that this study is being done correctly, and regulatory authorities where required by law. In addition, participants will be carefully informed about the Release of Health Information section in the ICF, which describes who will access their information and how it will be used. We will emphasize that participation in this study is voluntary and that participants can choose at any time to cease participation and revoke authorization to use and disclose their information.

14. Risks to Subjects

The risks below are associated with the use of the Oculus Quest 2 Virtual Reality Headset Device.

All adverse events (AEs) will be captured, and recorded at each time point. We will report AEs as a proportion of study participants who developed AEs.

Specific AEs to be monitored will include:

Neurological AEs: (defined as new-onset blurry vision, tingling, perioral numbness, seizures, or coma within 30 minutes after starting the study intervention)

Cardiovascular AEs: (defined as new-onset hypotension [SBP <90 mmHg and DBP <60 mmHg], bradycardia [HR < 50 bpm], tachycardia [HR >130 bsspm], or any new hemodynamic instability requiring more than two vasopressors after starting the study interventions

Pulmonary AEs: (defined as new-onset hypoxia [SpO2 < 88%] and/or hypercarbia [PCO2 > 60 mmHg] on arterial blood gas within 30 minutes of starting study interventions

Cardiac Adverse Events: New-onset hypotension (SBP <90 mmHg and DBP <60 mmHg), Bradycardia (HR < 50), Tachycardia (HR> 100), and Arrhythmias (Supraventricular or ventricular) with HR> 150 beats per minutes within 5 minutes after the starting of 3D Simulated VR sessions. Or changes >20% from baselines.

Pulmonary Adverse Events: New-onset hypoxia: SpO2 < 88%, Respirator rate > 35 breaths/minute within 5 minutes after the starting of 3D Simulated VR sessions.

Others:Rash, nystagmus, muscular hypertonicity, clonus or myoclonic jerks, and allergic reactions

If enrolled participants vital signs changes > 20% from baseline, the session will be stopped as it would be considered unsafe events

The safety precautions to minimize the risk to participants are as follows:

Vital signs BP, HR, RR, SPO2, and pain scores (using numeric pain rating scale tool) will be monitored before, during, and after using ReCognitionVR software.

15. Potential Benefits

No direct benefit to participants is anticipated. The data from this study is expected to inform on a subsequent clinical trial of the use of the ReCognition VR-based software in patients at risk for delirium.

16. Financial and Economic Issues

The participants in this study will not be compensated, and there is no additional cost to participants for taking part in this study.

17. Data Safety Plan

- The research team plans to periodically evaluate data collected regarding the benefits and harms of the study in order to evaluate the safety of the participants
- Data reviewed periodically will be the following:
 - Accuracy of the game/outcome
 - Adverse effects occurred during study intervention (ex. Seizures, nystagmus etc.)
 - Adverse effects post-24 hours of study intervention
 - Number of software and device re-starts and re-sets.
- Safety information will be collected during study visits and through telephone calls with participants

- Data collection will occur during the game. Specifically after the user plays the minigame in the ReCognitionVR Software. The software has been programmed to report the outcome to the research team once the user plays the minigame. Safety data collection will begin before the study intervention and also be collected 24 hours after study intervention.

All study data will be transmitted over an encrypted SSL (Secure Sockets Layer) connection that requires user authentication. This application is designed to be in full compliance with the International Conference on Harmonization and Good Clinical Practices (ICH-GCP), the FDA's Code of Federal Regulations (CFR) 21 Part 11 Electronic Record and Electronic Signatures, the FDA's "Guidance: Computerized Systems Used in Clinical Trials," and the Privacy Rule of the Health Insurance Portability and Accountability Act of 1996 (HIPAA).

HMRI policy on record retention will be followed, and human subject research data will be kept a minimum of 6 years after the completion of the study. Research materials will be stored in \ on password-protected computer systems on a secure server on the Houston Methodist network.

The roles and responsibilities of the Investigators (a) assuring that the trial is conducted according to the Protocol and MOP; (b) identifying, recruiting, and enrolling participants; (c) obtaining informed consent from each participant and protecting their rights; (d) collecting and entering study data into REDCap, and following participants through study completion: (e) assuring regular IRB/REB review.

18. Informed Consent Documentation and Process

Informed consent will be obtained in written format using a consent document that is HMRI-approved. The investigators involved in the consent process will all be credentialed at HMRI to participate in research at HMH. System Policy and Procedure RE-12 will be followed. The PI and investigators will identify healthy participants through public and randomized advertisement. Potential participants may also consent on the same day of use of ReCognitionVR software. During the informed consent process, the investigator or designee, who has been trained on the protocol, will explain the nature and scope of the intervention, potential risks, and benefits of participation and answer questions from the potential participants. All participants must sign and date the Institutional Review Board (IRB) approved informed consent form.

Additionally, the signed informed consent must be kept in the participant's medical records, and a copy must be given to the participant. During the informed consent process, the investigator and designee, who has been trained on the protocol, will explain the nature and scope of the intervention, potential risks, and benefits of participation and answer questions from the potential participants. Participants will be informed that the study is investigational and that their participation in the study is voluntary. They will be informed that they may refuse to participate or may withdraw consent to participate at any time, and for any reason, without jeopardizing their future care at this institution.

The PI and study team will ensure enough time to explain the ICF to the participants and answer all questions before signing the ICF. The study and the contents of the ICF will be explained in

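### Section 14 defines cardiac and pulmonary adverse events twice, with two tachycardia limits, unclear time windows and no combination rule, so the reported AE proportion is not fully defined

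*Combined protocol and SAP*

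**What the plan says.** Section 14 (Risks to Subjects) makes two commitments: "All adverse events (AEs) will be captured, and recorded at each time point", and "We will report AEs as a proportion of study participants who developed AEs". One lead-in sentence then introduces a set of definitions in which two body systems appear twice.

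- **Cardiovascular AEs (first cardiac item).** Hypotension, then "bradycardia [HR < 50 bpm], tachycardia [HR >130 bsspm", then instability needing vasopressors. The item applies from the start of the intervention and gives no closing time.
- **Cardiac Adverse Events (second cardiac item).** Hypotension, then "Bradycardia (HR < 50), Tachycardia (HR> 100), and Arrhythmias (Supraventricular or ventricular) with HR> 150 beats per minutes within 5 minutes after the starting" of the session. A separate sentence adds "Or changes >20% from baselines".
- **Pulmonary AEs (first pulmonary item).** SpO2 <88% and/or PCO2 >60 mmHg "on arterial blood gas within 30 minutes of starting study interventions".
- **Pulmonary Adverse Events (second pulmonary item).** "New-onset hypoxia: SpO2 < 88%, Respirator rate > 35 breaths/minute within 5 minutes after the starting of 3D Simulated VR sessions".

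The section's rule for ending a session uses the same relative change: "If enrolled participants vital signs changes > 20% from baseline, the session will be stopped as it would be considered unsafe events".

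The Schedule of activities (Section 5) places heart rate variability, SpO2, respiratory rate and blood pressure at pre, 10 minutes and post. It has no row for heart rate itself. The safety precautions at the end of Section 14 say that heart rate is among the signs monitored before, during and after use.

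**The concern.** A proportion of participants with AEs needs one rule that turns a participant's readings into yes or no. Section 14 gives two tachycardia limits and two pulmonary definitions. It does not say which governs, whether meeting either is enough, or whether the two sets serve different purposes. Two analysts holding the same readings could report different proportions, and a choice made after the data are in would be post hoc. The result is meant to inform a later trial in patients at risk for delirium, so its safety summary should be reproducible.

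**Working it through.** The plan states no AE rate, so there is no figure to reproduce. The check compares the definitions and then classifies a few example readings.

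**Where the items agree and differ**

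- Hypotension, bradycardia (HR <50) and the SpO2 limit (<88%) are the same in both sets.
- Tachycardia is the only event with two numeric limits: HR >130 and HR >100.
- In the second cardiac item the 5-minute phrase follows the arrhythmia element. It may govern the whole item or that element only.
- The pulmonary items have the same structure. The 30-minute phrase may govern the whole first item or only blood-gas hypercarbia. The 5-minute phrase may govern the whole second item or only respiratory rate.
- The >20% sentence in the second cardiac item names neither variables nor a window. The session-stop sentence calls such changes unsafe events without saying whether they count as AEs.

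**Example readings**

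The values are illustrative and are not taken from the documents. Changes from baseline:

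- HR: 105/90 − 1 = +16.7%
- SpO2: 87/96 − 1 = −9.4%
- SBP: 88/100 − 1 = −12.0%; DBP: 58/65 − 1 = −10.8%

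All are under 20%, so none of the classifications rests on the relative clause.

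| Reading | First item | Second item, 5-minute phrase covers whole item | Second item, phrase covers last element only | Either item counts |
|---|---|---|---|---|
| HR 90 to 105 at 4 min | no | yes | yes | yes |
| HR 90 to 105 at 10 min | no | no | yes | depends on phrase |
| SpO2 96 to 87 at 10 min | yes | no | yes | yes |
| BP 100/65 to 88/58 at 10 min | yes | no | yes | yes |

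The first row is an AE under the second item only, however the phrase is read. The second row stays open even if either item is enough. The last two rows resolve under a combined rule. Under the second item alone they depend on the phrase.

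**How wide the open band is**

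Suppose the >20% sentence covers heart rate and has no time limit. A 20% rise reaches HR 100 from a baseline of 100/1.2 = 83.3. From 83.3 or below, any HR over 100 is then already an AE. From a baseline of 90 the 20% mark is 90 × 1.2 = 108, so after 5 minutes an HR of 101 to 108 is open. If the clause does not cover heart rate, or is itself limited to 5 minutes, the band is wider.

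**Size per participant**

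Section 4 enrols 15 participants per age group, 30 in all, and analyses the groups separately. One reclassified participant moves the proportion by 1/15 = 6.7 points in a group, or 1/30 = 3.3 points overall.

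**Link to the measurements**

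The first scheduled reading after the start is at 10 minutes. No scheduled vital-sign reading can therefore meet a criterion limited to the first 5 minutes. The heart rate limits also have no scheduled row to draw on, although heart rate is monitored.

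**The case against.** The strongest reply is that the two sets form one list. They share a lead-in, follow a commitment to capture all AEs, and are nowhere presented as alternatives. That is the natural reading, and it settles three of the four examples. It is not stated, however. It would also make the HR >130 limit redundant beside HR >100 during the first 5 minutes, and it leaves the second example open. Capturing all AEs does not say which heart rate is one.

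A second reply is that the remaining gap is narrow, because the >20% sentence already catches most rises past 100 from a low baseline. That holds if the sentence covers heart rate without a time limit, which the text does not say. A >20% fall in SpO2 takes the value below 80%, so it meets the <88% limit anyway; the uncertainty about that clause bears little on SpO2.

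Several stronger inferences are tempting, and the documents do not support them:

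- **Each list catches events the other misses.** The heart rate example at 4 minutes shows one direction. The SpO2 example does not establish the other, because the 5-minute phrase may attach to respiratory rate alone.
- **The schedule contradicts the promise to record AEs at each time point.** The Time 4 entry is a review and evaluation, which can coexist with earlier recording.
- **The data list in Section 8 shows that heart rate will not be collected.** That list also omits blood pressure, which the schedule includes, so its silence proves nothing.
- **No reading will be taken in the first 5 minutes.** Section 14 says vital signs are monitored during use, without restricting this to 10 minutes. Only the scheduled readings start there.
- **The 24-hour safety collection in Section 17 is part of this problem.** Its fit with a one-day schedule is a separate question.

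**Conclusion.** The point holds and is minor. Section 14 states two tachycardia limits and two pulmonary definitions for one reported proportion, with no precedence or combination rule and with time phrases of uncertain reach. Combining the lists removes most of the ambiguity but not all of it: HR 90 to 105 at 10 minutes is still an AE on one reading and not on the other.

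The size is 6.7 points per reclassified participant in a group of 15, or 3.3 points of 30. This is a step size and not a predicted error. The documents give no basis for how many participants would be affected, and any count would rest on assumed heart rates.

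A reader might infer that the trial's endpoints are compromised. They are not. The primary endpoint is 20 minutes of use, and the listed tertiary safety endpoints in Section 2 are mean changes in vital signs. Neither definition uses these AE lists, the analysis is descriptive, and no decision rule depends on the AE proportion.

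**What to change.** Before enrolment, the sponsor's clinical team should:

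1. Reconcile the duplicated cardiac and pulmonary items in Section 14 into one AE list, with one threshold and an unambiguous window per event.
2. State whether a >20% change from baseline counts as an AE, and for which measures.
3. Align the Schedule of activities and the CRF so that every retained criterion has a recorded measurement, including the heart rate already monitored.

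Which limits, windows and criteria to keep is for the clinical team. The cost is a wording, schedule and CRF edit. The reported AE proportion may move in either direction as a result.

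### Section 14's only written session stop, a change in vital signs of more than 20% from baseline, cannot act on a fall in SpO2 until it is below 80%, at least 8 points under the protocol's own hypoxia limit of 88%

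*Combined protocol and SAP*

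**What the plan says.** Section 14 (Risks to Subjects) of the combined protocol and SAP does three things that bear on this point.

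- **It sets one stop rule.** "If enrolled participants vital signs changes > 20% from baseline, the session will be stopped as it would be considered unsafe events". The same percentage applies to every vital sign. Another mention of a change above 20% in Section 14 belongs to the cardiac adverse event definition and does not stop a session.
- **It lists the vital signs.** "Vital signs BP, HR, RR, SPO2, and pain scores (using numeric pain rating scale tool) will be monitored before, during, and after" use of the software. SpO2 is therefore covered by the stop rule.
- **It defines hypoxia as an adverse event, twice, at the same value.** The first pulmonary definition reads "defined as new-onset hypoxia [SpO2 < 88%] and/or hypercarbia", within 30 minutes of starting. The second reads "New-onset hypoxia: SpO2 < 88%, Respirator rate > 35 breaths/minute within 5 minutes after the starting of 3D Simulated VR sessions".

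The stated consequence of an adverse event is recording and reporting: "All adverse events (AEs) will be captured, and recorded at each time point", and "We will report AEs as a proportion of study participants who developed AEs". No definition in Section 14 says that the session must end when its limit is reached. Section 12 (Withdrawal of Subjects) lets the participant or the principal investigator end participation but gives no safety threshold. The Schedule of activities in Section 5 places pulse oximetry at pre-session, 10 minutes and post-session.

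**The concern.** A single percentage works differently on different scales. Heart rate and respiratory rate can move by 20% with modest exertion. SpO2 in a healthy person starts near the top of a scale that ends at 100%, so a 20% fall is a very large one. A rule that is cautious for respiratory rate may thus be lax for oxygen saturation.

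If the stop lies below the value that the protocol itself calls hypoxia, a participant can meet the adverse event definition while the written rule gives no instruction to stop. That errs in the unsafe direction. It also matters for what follows: under Sections 2 and 4 the results and the safety measures are to inform a later study in patients at risk for delirium.

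**Working it through.** **Inputs.** From Section 14: stop at a change above 20% from baseline; hypoxia at SpO2 <88%; bradycardia at HR <50 bpm; hypotension at SBP <90 and DBP <60 mmHg; respiratory rate limit >35 breaths/minute. The documents give no baseline SpO2 values. The main result needs only the physical maximum of 100%; baselines of 98% and 95% are assumed for illustration. The plan states no SpO2 stop value, so there is no figure of its own to reproduce.

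**Step 1: where the rule acts on a fall in SpO2.**

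Relative reading: stop when SpO2 < 0.80 × baseline. Percentage-point reading: stop when SpO2 < baseline − 20. Gap = 88 − stop value.

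| Baseline | Relative: stop below | Gap | Points: stop below | Gap |
|---|---|---|---|---|
| 100 | 0.80 × 100 = 80.0 | 8.0 | 80 | 8 |
| 98 | 0.80 × 98 = 78.4 | 9.6 | 78 | 10 |
| 95 | 0.80 × 95 = 76.0 | 12.0 | 75 | 13 |

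The gap is smallest at a baseline of 100 and widens as the baseline falls.

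**Step 2: could any baseline close the gap?** For the stop to lie at 88, the baseline would have to be 88 / 0.80 = 110% (relative) or 88 + 20 = 108% (points). Both are impossible. A relative rise above 20% would need a baseline below 100 / 1.20 = 83.3%, already under the hypoxia limit, so upward changes do not help.

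**Step 3: readings that are an adverse event but not a stop (relative reading, whole numbers).** Baseline 100: 80 to 87, 8 values. Baseline 98: 79 to 87, 9 values. Baseline 95: 76 to 87, 12 values. A reading of 87% is hypoxia by definition, but a change of only 13/100 = 13.0%, 11/98 = 11.2% or 8/95 = 8.4%.

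**Step 4: the other vital signs.** The rule can miss a lower limit L only when 0.80 × baseline < L, that is, when baseline < L / 0.80.

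- HR: 50 / 0.80 = 62.5 bpm. Example: 55 to 48 is bradycardia, but 7/55 = 12.7%, so no stop.
- BP: 90 / 0.80 = 112.5 and 60 / 0.80 = 75 mmHg. Section 14 joins the two limits with an and, so both baselines must be under these values. Example: 100/70 to 85/58 is hypotension, but the changes are 15/100 = 15.0% and 12/70 = 17.1%, so no stop.
- Respiratory rate: from an assumed 16, the rule acts above 16 × 1.20 = 19.2, well before 35.

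SpO2 is thus the only one of these signs with the gap at every baseline. The contrast is plain: a respiratory rate rising from 16 to 20 (25%) must stop the session, while SpO2 falling from 98 to 79 (19/98 = 19.4%) need not.

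**Step 5: what an absolute stop costs the primary endpoint.** Each session stopped before 20 minutes lowers the maximum completion in a group of 15 by 1/15 = 6.7 points. If everyone else completes, 4 stops leave 11/15 = 73.3% and 5 leave 10/15 = 66.7%, against the 70% target.

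**The case against.** The strongest reply is practical. Participants are ASA 1 or 2 volunteers (Section 10) doing one session of about 20 minutes at low cognitive load (Section 5), so SpO2 below 88% should be rare. Nothing tells staff to continue when an adverse event limit is reached. A change above 20% in heart rate, respiratory rate or blood pressure could stop the session. The investigator may withdraw a participant, and the reasons in Section 12 are only examples. The participant can also leave: "A participant may discontinue his or her participation without giving a reason at any time during the study". No endpoint or sample size depends on the gap. All of this stands and limits the practical effect. None of it is a written SpO2 safeguard.

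Four stronger readings are tempting, and the documents do not support them.

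- A reader might infer that a participant with hypoxia would be kept in the session. The text only fails to require a stop; the other routes out remain.
- A reader might infer that SpO2 is the only sign with this fault. Heart rate and blood pressure share it at lower baselines.
- A reader might infer that the faulty limit will pass into the later trial. Section 2 says that results will inform its design, not that this rule will be reused.
- A reader might infer that reasons for early stopping will go unrecorded. The case report forms are not in the documents, and Section 17 reviews adverse effects and the "Number of software and device re-starts and re-sets". That question is separate from the SpO2 limit and forms no part of this point.

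**Conclusion.** The point holds. As written, the stop cannot act on a fall in SpO2 until it is below 80%, at least 8 points under the protocol's own hypoxia limit, at any baseline and under either reading of 20%. This rests on the Section 14 text and the 100% ceiling alone; only the wider gaps of 9.6 to 13 points depend on assumed baselines of 98% and 95%. The gap in heart rate and blood pressure is real but conditional on low baselines.

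The documents give no rate of SpO2 below 88% in such volunteers, so the number affected cannot be computed and is probably small. The mismatch is nevertheless certain, lies in the unsafe direction and is cheap to correct, so it should be corrected before the rule is relied on.

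**What to change.** Keep the 20% rule and add to the stop sentence in Section 14: or SpO2 <88% (or a higher value set by the clinical team). From baselines of 100, 98 and 95, a fall to 88 is 12/100 = 12.0%, 10/98 = 10.2% and 7/95 = 7.4%, so the new clause would act well before the present one. Consider adding the Section 14 bradycardia and hypotension limits to the same clause.

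State that the clause applies to every SpO2 reading taken during the session. The Schedule of activities fixes only one in-session reading, at 10 minutes, and Section 14 does not say that monitoring is continuous. If the 10-minute reading is the only one, the new stop can act just once in the session.

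The cost is one clause. It needs no more participants or visits and, if applied to readings already planned, no new measurements; more frequent in-session readings would be an addition. The downside is possibly a few more stopped sessions.
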